Mindfulness During Coronavirus

IRB00064587

8.12.2020

NCT04319445

Principal Investigator: [name] [name], MPH, Associate [name] of Neurology, Wake Forest University Health Sciences

Mindfulness During Coronavirus

Principal Investigator: [name] [name], MPH, Associate [name] of Neurology, Wake Forest University Health Sciences

Supported by: Wake Forest Baptist Medical Center Department of Neurology, Headache Program

Study Intervention Provided by: N/A

Sponsor of IND (IDE): N/A

Study Site

Wake Forest School of Medicine

Department of Neurology

Objective:

The objective of our study is to provide remote mindfulness session(s) to help during the COVID-19 pandemic. We are interested in targeting patients with migraine, providers, faculty and staff. We are hopeful that this will positively impact overall well-being at this stressful time. We are interested in assessing feasibility, accessibility, and overall interest of an online mindfulness intervention in these populations at this time.

Background & Rationale:

With the COVID-19 pandemic ongoing, anxiety, stress, and uncertainty is at an unprecedented level. Further, in order to prevent transmission and further spread, "social distancing" is recommended, which can lead to isolation and a sense of helplessness.

Mindfulness meditation is a treatment approach that can target anxiety and stress.[1] Mindfulness practice teaches individuals to focus on the present moment.[2] Mindfulness is an intervention that can be taught remotely, over the phone, or online. A meta-analysis of 15 RCTs showed that online mindfulness based interventions (MBIs) have a positive effect on depression, anxiety, and well-being. [3]

Stress is the number one trigger for migraine, [4-7] so targeting stress is important for patients with migraine.[8] Mindfulness may be helpful for patients with migraine.[9]

Providers, faculty and staff are also under tremendous stress during this pandemic, with the additional stressor of setting up an effective remote work environment and making decisions about priority of care. Mindfulness may be helpful for working adults as well.[10]

The PI has experience conducting research with this intervention, having conducted three randomized controlled trials of a mindfulness intervention; two in adults with migraine and one in adults with mild cognitive impairment.

Methods:

Recruitment:

Migraine patients:

Potential migraine participants will be notified in a multitude of ways. We will send a MyWakeHealth message of this opportunity. We will also recruit online via social media, MigraineWorldSummit, and other online avenues to patients in the Winston Salem area and across the country. Other healthcare providers across the country may be interested in sharing this with their patients as well.

Interested participants can click on a link that will take them to a REDCap survey. Or they can email us at the [contact] email account expressing their interest and we can then notify them of the details of the mindfulness session. Participants will be consented with this statement at the beginning of the survey document, "These surveys are completely voluntary... By proceeding with this survey, you are agreeing to participation."

Providers/Faculty/Staff:

Potential providers/faculty/staff will also be notified of this opportunity with online recruitment (through a variety of mechanisms, including Intranet, email, etc). A link to the survey will be included in the online recruitment/announcement, or they can respond to us via email. We will then notify them of the details of the mindfulness session.

Others interested:

Nearly everyone has been affected by this pandemic, and anyone may find benefit from this mindfulness session. The session will be made available more broadly to the public via social media, email, and other online resources.

ResearchMatch.org will be utilized as a recruitment tool for this protocol. ResearchMatch.org is a national electronic, web-based recruitment tool that was created through the Clinical & Translational Science Awards Consortium in 2009.

Mindfulness session(s)

The sessions will be hosted online using an online platform (such as through webex, private YouTube page, Facebook live, etc). The sessions may be live or pre-recorded. The live sessions will be recorded and may be made publically available. For the first live session, all those who participated will be contacted to sign a consent acknowledging and releasing the matieral to be made publically available. For future live sessions, the main consent form has been adjusted to include this information.

We will begin with an initial session and assess level of interest in order to determine whether to continue with follow-up sessions on a daily, weekly, or monthly basis.

Information about additional sessions will be made available to participants who have already participated in the first session, and may be advertised to new participants as well.

Assessments:

We will assess value and interest of this type of intervention using this platform with a pre-post survey. The participants will complete the surveys via REDCap. Links to the surveys via

REDCap will be available in the announcements/recruitment information and/or sent to their emails. Data will be stored via REDCap electronic data system. Each participant will create a unique identifier number to ensure matching of all pre/post surveys completed by that participant. If a participant completes a pre-survey but not a post-survey, they may be emailed to thank them for their participation and sent the link to complete the post-survey as a reminder.

Pre/post surveys may be available for each mindfulness session.

A single post-survey will also be sent after the live sessions to assess participants overall experiences with the live mindfulness sessions.

Participant Selection:

Any person interested in participating in the mindfulness session will be eligible to complete the pre/post surveys and participate in the mindfulness session(s).

Sample Size

The estimated sample size for survey completion is 200. This is the number of individuals who are expected to participate in the mindfulness session and complete the surveys, although online recruitment is highly variable and may result in more participants than expected.

Human Subjects Protection

Informed Consent

Participants will be informed of the voluntary nature of the surveys at the beginning the survey. Participants will be informed of the possibility of additional mindfulness sessions and surveys, so that the original consent will include participation in additional sessions/surveys. Written informed consent will not be obtained.

Risks

The risk of harm or discomfort that may occur as a result of taking part in this research study is not expected to be more than in daily life or from routine physical or psychological examinations or tests. This study overall poses minimal risks. The intervention of mindfulness is a non-drug intervention with rare side effects. The recruitment, surveys, and intervention will all be conducted remotely to avoid face-face interaction during this time of the COVID-19 pandemic. The rights and welfare of study will be protected through the use of measures to maintain the confidentiality of study information.

Confidentiality and Privacy

Confidentiality will be protected by collecting only information needed to assess study outcomes, minimizing to the fullest extent possible the collection of any information that could directly identify subjects, and maintaining all study information in a secure manner. To help ensure subject privacy and confidentiality, only a unique study identifier will be assigned to each data collection form. Any collected patient identifying information corresponding to the unique study identifier will be maintained on a separate master log. The master log will be kept secure, with access limited to designated study personnel. Following data collection subject identifying information will be destroyed at the earliest opportunity, consistent with data validation and study design, producing an anonymous analytical data set. Data access will be limited to study staff. Data and records will be kept locked and secured, with any computer data password protected. No reference to any individual participant will appear in reports, presentations, or publications that may arise from the study.

Data and Safety Monitoring

The principal investigator will be responsible for the overall monitoring of the data and safety of study participants. The principal investigator will be assisted by other members of the study staff.

REFERENCES:

- [1] Ludwig DS, Kabat-Zinn J (2008) Mindfulness in medicine. *Jama* **300**, 1350-1352.
- [2] Kabat-Zinn J (1990) Full Catastrophe Living: Using the WIsdom of Your Body and Mind to Face Stress, Pain, and Illness, Random House, New York.

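### Does open eligibility conflict with an Objective that names migraine patients and providers, faculty and staff?

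*Protocol*

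**What the plan says.** The Objective begins with a general aim of offering remote mindfulness sessions during the pandemic. It then names the groups of interest: "We are interested in targeting patients with migraine, providers, faculty and staff". Two sentences later it states what will be assessed, and in whom: "We are interested in assessing feasibility, accessibility, and overall interest of an online mindfulness intervention in these populations at this time".

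Recruitment has three headings. Two match the groups in the Objective. The third, Others interested, adds the public: "The session will be made available more broadly to the public via social media, email, and other online resources". Some channels overlap. For migraine patients the protocol says "We will also recruit online via social media, MigraineWorldSummit, and other online avenues to patients", so social media serves both patients and the public. Email is named for staff and for the public. The registry is not tied to any one group: "ResearchMatch.org will be utilized as a recruitment tool for this protocol".

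Participant Selection applies no group criterion: "Any person interested in participating in the mindfulness session will be eligible to complete the pre/post surveys". Sample Size gives one number: "The estimated sample size for survey completion is 200". It explains this as the count expected to take part and complete the surveys, and adds that online recruitment is variable and may bring in more.

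On continuing the programme, the section on the mindfulness sessions says: "We will begin with an initial session and assess level of interest in order to determine whether to continue with follow-up sessions".

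Confidentiality and Privacy limits collection to what the study outcomes need, and has identifying information destroyed after data collection so that the analysis data set is anonymous.

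**The concern.** A protocol should make clear in whom its question is asked, and its eligibility and sample size should refer to those same people. Here the assessment question is tied to two named populations, while anyone may enter and the total is not divided. If many completers were members of the public, fewer than 200 people would bear on the question as worded, and the protocol gives no indication how many fewer.

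A practical worry follows. Because the channels overlap, the route by which someone arrived does not reveal their group. If the survey did not ask, and identifiers were then destroyed, respondents could not be sorted afterwards, and no SAP could recover a variable that was never collected. The decision on follow-up sessions could also rest on interest in an undefined mix of people.

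**Working it through.** **The stated figure.** The 200 cannot be reproduced, and it does not need to be. Sample Size presents it as expected uptake. The protocol gives no error rate, power, effect size, variance or precision target from which it could be derived, so there is no calculation that a different population mix would invalidate.

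**How many might come from the named groups.** Let w be the share of completers from the general public. The protocol does not give w, so the values below are assumptions. The named groups together supply n = 200 × (1 − w). For scale, the half-width of a 95% confidence interval for a proportion in the worst case (p = 0.5) is 1.96 × √(0.25/n).

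| Assumed w | n = 200 × (1 − w) | Half-width |
|---|---|---|
| 0 | 200 | 6.9 points |
| 0.25 | 150 | 8.0 points |
| 0.50 | 100 | 9.8 points |
| 0.75 | 50 | 13.9 points |

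The full range for n is 0 to 200, but that is true of any unquantified subset of any sample. The table describes precision under assumed shares. It does not show an error, because the protocol sets no precision target that any row could miss.

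**The sections side by side.**

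1. *Objective against Participant Selection.* The Objective speaks of targeting, opens with an unrestricted aim, and nowhere says that only these groups will be studied. Targeting some groups while admitting anyone is consistent. What remains is that the assessment sentence refers to the named populations and leaves out the public, who are also surveyed.

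2. *Whom the 200 counts.* Participant Selection makes any interested person eligible. Sample Size, the next section, counts those expected to take part and complete the surveys. Read in order, the 200 covers all comers, and a sentence saying so would repeat what the text already conveys.

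3. *Whose interest decides on further sessions.* The sessions are open to anyone. Information about further ones goes to earlier participants and may be advertised to new ones. This is an operational decision about running an open programme, and interest among all comers is its natural basis. No decision confined to the named groups depends on it.

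4. *Whether respondents can be sorted.* The destruction rule in Confidentiality and Privacy concerns information that identifies individuals. Being a migraine patient or a staff member does not in itself do that. The same section permits collecting what the outcomes require, and an Objective that names these groups makes a group item readily justifiable. The survey items are not reproduced in the protocol and may already include one.

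**The case for a change.** The strongest case for a change is that Objective, eligibility and sample size are all protocol content, so a mismatch among them cannot simply be passed to the SAP. Intending to include the public explains the eligibility rule but does not make the stated question cover the public. The Background supports the narrower reading: its specific arguments concern migraine patients and then providers, faculty and staff. Group membership has to be captured during data collection, because participants can go straight from a link to the survey under an identifier they create themselves. The remedy would be cheap: a few sentences and at most one survey item, with no extra enrolment.

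Some of this stands. The Objective is not worded to match eligibility, and it is true that a variable that was not collected cannot be recovered. The second point becomes a defect, however, only if the survey omits the item, and the protocol neither shows nor implies that it does. Reporting by group is ordinary SAP content. An expected number for each group would add little where uptake is, by the protocol's own account, highly variable and no test or precision target depends on it. That a change is cheap does not create a need for it when nothing in the analysis or interpretation would improve.

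**Conclusion.** The concern identifies a real looseness of wording and nothing more. The Objective names migraine patients and providers, faculty and staff; the rest of the protocol deliberately and openly admits the public as well. Naming the public in the Objective would be a harmless editorial tidy-up, but no design feature, figure or analysis depends on it.

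The size is undetermined: 150, 100 or 50 of the 200 from the named groups if the public's share is 25%, 50% or 75%, all of them assumed shares. No bias is shown, because the document fixes neither the public's share nor any difference between groups, and it does not say that groups will be pooled.

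The conclusion rests on two readings: that targeting does not mean excluding others, and that the 200 counts everyone eligible. It also assumes that analysts will describe respondents by group where the survey allows, a sensible default for a minimal-risk survey study with no stated hypothesis test. If the survey proved not to record group, results could be described only for all comers, and a statement confined to the named groups would not be supported. The protocol gives no ground for supposing that this is so.

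### The eligibility rule admits any person with no age limit, so as written minors can enrol through public links on their own agreement

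*Protocol*

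**What the plan says.** Participant Selection is a single sentence. It begins "Any person interested in participating in the mindfulness session will be eligible" and goes on to cover both the surveys and the sessions. It has no minimum age and no exclusion.

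On access, the Recruitment part of Methods names social media, a national recruitment website and other online channels, and says "The session will be made available more broadly to the public via social media, email, and other online resources". The Assessments section says that links to the surveys via "REDCap will be available in the announcements/recruitment information and/or sent to their emails".

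On consent, Recruitment gives the statement that opens the survey, shortened by an ellipsis and ending "By proceeding with this survey, you are agreeing to participation". The Informed Consent section adds "Written informed consent will not be obtained", and says that the original consent extends to further sessions and surveys.

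On who the study is for, the Objective says "We are interested in targeting patients with migraine, providers, faculty and staff". Background & Rationale says "Mindfulness may be helpful for working adults as well" and describes the investigator's three earlier trials, all in adults. Recruitment then widens the scope: it reasons that the pandemic has touched almost everybody and that the session could help all comers.

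**The concern.** An eligibility rule fixes two things: who may be exposed to the study procedures, and what population the results describe. Here the rule is explicit and has no lower age bound, while the way in is an open link that a teenager could follow from social media. The consent step described works for someone who can consent alone. The protocol text does not say what happens when that is not so.

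Two other provisions raise the stakes. Live sessions are recorded and may be released publicly. For sessions after the first, that release is built into the main consent form, so a minor could be asked to accept it unaided. Identifying information is also to be destroyed as early as is feasible, leaving an anonymous analysis file. The protocol does not say whether the surveys ask for age, so a respondent's age may be hard to establish later. A check at entry is worth more than one at analysis.

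**Working it through.** No arithmetic applies. The only number in the design is an expected 200 survey completers. It is a forecast of turnout with no calculation behind it, so there is nothing to reproduce. The check is to follow a 16-year-old respondent (a hypothetical case) through the plan as written.

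1. **Reaching the link.** The Recruitment and Assessments sections place survey links in announcements, and the session is offered to the public. Nothing limits the announcements to adult audiences. The alternative route, writing to the study's email account, leads to session details being sent, with no screening described.

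2. **Eligibility.** Participant Selection asks only for interest. The respondent qualifies.

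3. **Consent.** Proceeding with the survey is agreement, and written consent is not sought. The same agreement carries over to later sessions and surveys. The protocol text describes no age question, parental permission, assent or waiver.

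4. **Live session.** The respondent may join, and the session is recorded. For the first live session, those who took part are to be contacted to sign a release. For later ones, the main consent form covers it. The signed release concerns the recorded material, not enrolment, and no age is attached to it.

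5. **Analysis.** Completed surveys are matched by a self-created identifier and identifiers are later destroyed. Nothing shown removes this respondent.

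The same steps were then read for text that would stop this respondent. Two places could. The survey's consent statement contains an ellipsis, so part of its wording is not visible. The main consent form is mentioned but not shown. An age attestation could be in either. If one is there, it would conflict with a rule that admits any person. If instead the unseen text provides for parental permission, it would not conflict with the rule, but the protocol should refer to it.

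The stated population can be compared in the same way:

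| Place in the protocol | Age stated |
|---|---|
| Objective, migraine patients | None |
| Objective, providers, faculty and staff | None, but an employed group |
| Background & Rationale, workplace evidence | Adults |
| Background & Rationale, investigator's earlier trials | Adults |
| Recruitment, others interested | None; open to all |
| Participant Selection | None; any person |

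Wherever an age group is given it is adult, but no line makes the study adults-only.

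**The case against.** The strongest reply is that broad entry is deliberate. The study assesses feasibility, accessibility and interest, the intervention is described as minimal risk, and the Recruitment section openly extends the offer to everyone. On that reading, admitting any person is consistent with the plan.

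Much of this stands. A reader might infer that the protocol contradicts itself by enrolling minors in a study reasoned for adults. The document does not support that. The remark about working adults closes the paragraph on providers, faculty and staff and supports that group only. The earlier trials are cited as the investigator's experience, not to define the population. Migraine patients carry no age anywhere.

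A reader might also infer that minors have no route to parental permission. That cannot be asserted either, given the shortened consent statement and the unseen consent form.

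The reply does not remove the core. If breadth was meant to include minors, the protocol should say how they are consented. If it was not, the rule should exclude them. Minimal risk lowers the urgency but does not supply a consent process.

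**Conclusion.** The point holds as one about a stated rule. Participant Selection sets no age limit, entry is by public link, and the only entry consent described is proceeding with the survey. As written, minors can enrol on their own agreement and take part in recorded sessions. It should be corrected, in proportion to a minimal-risk survey study.

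The conclusion rests on the protocol text alone and assumes nothing about the consent wording that is not shown. If an age attestation exists there, what remains is to reconcile it with the eligibility sentence.

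Two further readings go beyond the document. One is to put a number on the minors enrolled. The protocol gives no age distribution, so any share applied to the 200 would be invented, and no figure is offered. The other is that minors' records would be unusable and would have to be dropped after the data are seen. Nothing in the document says so, and the point does not need it.

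**What to change.** Amend the Participant Selection sentence so that it opens with any adult (aged 18 years or older) in place of any person. Add a required age-confirmation item before the REDCap survey that ends it for respondents under 18.

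If minors are intended, leave the rule open but say so, and describe parental permission and assent, or the waiver that applies, including for the release of recordings.

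In either case, make the survey's consent statement and the main consent form agree with the rule.

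The cost is one amended sentence and one branching item. The downside of the adults-only version is small: a few young respondents are not counted. The survey item also has a limit, since it does not control who watches sessions that are posted publicly.

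### Does ruling out written consent contradict the signed release planned for recorded live sessions?

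*Protocol*

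**What the plan says.** Three parts of the protocol bear on consent.

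- **Recruitment.** Consent to the surveys is given by a statement at the start of the REDCap survey. Proceeding counts as agreement, and no signature is involved.
- **Mindfulness session(s).** On recording: "The live sessions will be recorded and may be made publically available". For the session already singled out: "For the first live session, all those who participated will be contacted to sign a consent acknowledging and releasing" the material for public use. For later ones: "For future live sessions, the main consent form has been adjusted to include this information". The same section adds: "Information about additional sessions will be made available to participants who have already participated in the first session".
- **Human Subjects Protection, Informed Consent.** Participants are told of possible further sessions and surveys, "so that the original consent will include participation in additional sessions/surveys. Written informed consent will not be obtained". The section states no exception.

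The Assessments section is also relevant, because it leaves repeat surveys optional: "Pre/post surveys may be available for each mindfulness session".

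**The concern.** Two things look wrong on a first reading.

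First, the section that governs consent excludes a written one outright, yet another section has people sign a document that the protocol itself calls a consent. Staff following one sentence would appear to breach the other.

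Second, the original consent is said to carry forward to later sessions, while the recording information for those sessions sits in a form that was changed afterwards. A person who agreed under the older wording and then returns for a later live session might never have seen the recording text. The signed release is described for the first live session only, and a survey that would show the consent statement again is not guaranteed at each session.

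What would be at stake is whether attendees had agreed to a recording that might be made public. It would not be any estimate from the pre/post surveys.

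**Working it through.** No formula applies and the plan has no figure to reproduce on this point. The check is to set the consent statements side by side and ask, for each pair, whether both can be true.

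| Statement (section) | Subject | Who | Signature |
|---|---|---|---|
| Opening survey statement (Recruitment) | Surveys | Anyone opening the survey | No |
| Original consent carries forward (Informed Consent) | Participation in further sessions and surveys | All participants | No |
| No written consent (Informed Consent) | Not limited in words; the section discusses only surveys and sessions | All participants | No |
| Release (Mindfulness session(s)) | Public use of a recording | First live session attendees | Yes |
| Adjusted main form (Mindfulness session(s)) | Same recording information | Future live sessions | Not stated |

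**Pair 1: no written consent against the signed release.** If the exclusion covers every kind of agreement in the study, the two conflict. If it covers consent to take part, which is all the Informed Consent section discusses, both are true. The second reading fits better. The section mentions surveys, further sessions and further surveys, and never recordings, while the session text states what the signature is for. A specific instruction about one recording, placed beside a general statement about participation, is ordinarily read as an exception to it. The slip is the missing limiting phrase.

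**Pair 2: original consent against the adjusted form.** The first extends to participation in later sessions. The second concerns recordings and their possible release. A person can have agreed to attend further sessions without having agreed to release of a recording, so both statements hold together. This is not a contradiction.

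**What the text settles for each kind of attendee.**

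1. Attended the first live session, for that recording: signed release.
2. New at a later live session: adjusted form.
3. Consented before the adjustment and attends a later live session: the adjusted form is described by session, not as being for newcomers only, so on its face it applies to this person too. How it reaches them is not stated. A repeat survey opening with the consent statement is one route, but repeat surveys are optional.

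Only case 3 is open, and it is open on procedure, not on principle. The protocol gives neither first-session attendance nor a return rate, so the group cannot be counted. The 200 in the Sample Size section is the expected number of survey completers and says nothing about returners.

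**Effect on the analysis.** The sample-size expectation and the matching of pre and post surveys do not depend on which document records agreement to a recording. The effect on estimates, precision and bias is nil.

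**The case for a change.** The strongest case for acting runs as follows. The protocol calls the signed document a consent, and for later sessions it moves the same content into the main consent form. It therefore treats agreement to recording as part of study consent, not as a media release outside the Informed Consent section. Yet that section never mentions recording, and neither does the Confidentiality and Privacy section. By seeking agreement from every first-session attendee, the study team shows that it regards agreement as needed. A returning participant is then carried forward under old wording, and no sentence requires the new wording to be shown. A few sentences would settle it at almost no cost.

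Part of this stands. The sentence excluding written consent is worded too broadly. The protocol also does not say whether the main consent form is the unsigned survey statement or a separate document, or how earlier participants meet the adjusted text.

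The rest does not carry. The claim that staff could not tell who had agreed supposes that they work from two protocol paragraphs and have no consent records. The claim that earlier participants are not asked again cannot be tested, because the consent form is not available here and the survey statement is quoted only in abridged form. Public release is also described as possible, not required, so nothing in the text forces release of a recording for which agreement is incomplete.

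**Conclusion.** No change to the plan is called for. One of the two alleged conflicts is a real but narrow clash of wording, a clerical slip in which a general sentence lacks the exception stated elsewhere. The other is a gap in procedural detail that the study team can fill sensibly from the adjusted form and its own consent records. Neither alters the expected 200 survey completers, any survey estimate, its precision, or the conclusions.

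This rests on two assumptions: that the signed document is confined to the recording, as the session text describes, and that the adjusted form is put to anyone joining a later live session, as its session-based wording suggests. If the second proved false, the matter would be one of consent administration for the study team and its ethics board, still with no statistical consequence. A limiting clause in the Informed Consent section would be reasonable housekeeping if the protocol were being revised for other reasons, but the point does not justify a revision by itself.
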